**Table 2. Vital Signs: Reference Values**

	Reference Values
SBP (mmHg)	90 ≤ SBP ≤ 120 mmHg
DBP (mmHg)	60 ≤ DBP ≤ 90 mmHg
Heart Rate (beats/min)	60 to 100 beats/min
Body Temperature (°C)	35.5 to 37.5 °C

### 8.7.4. Electrocardiograms

The ECG results will be listed per subject as “normal” or “abnormal”. All abnormalities will be classified in terms of clinical relevance (CR, NCR). Clinically relevant abnormalities will be reported as AEs.

#### 8.7.5. Physical Examinations

Clinically relevant changes from screening in physical examination will be reported as AEs.

#### 8.7.6. Previous and Concomitant Medications

All other medications used will be listed as concomitant medications.

Previous/Concomitant medications will be coded according Anatomical Therapeutic Chemical (ATC) classification system.

#### 8.8. Plasma Concentrations

████████████████████ will carry out the determination of plasma levels of cytisine in accordance with the applicable principles of Good Laboratory Practices (GLP), using a previously validated LC-MS/MS analytical method. The pre-planned lower limit of quantification (LLOQ) is 1 ng/mL and the upper limit of quantification (ULOQ) is 400 ng/mL.

Individual (per subject) and mean plasma concentration versus time profiles will be presented for both linear and semi-logarithmic scales. Graphic presentation of individual data will be based on actual blood sampling time, except for pre-dose sampling time which will be assumed as t0.

Descriptive statistics (number of subjects, geometric mean, arithmetic mean, SD, CV%, median, minimum and maximum) of the plasma concentrations will be presented for each time point. Concentrations below the LLOQ will be taken as missing for the calculation of geometric mean and replaced by zero for calculation of the remaining summary statistics.

The pre-dose blood samples were to be collected within 30 minutes prior to dosing. The post-dose blood samples were to be collected within +/-2 minutes from the scheduled sampling time. The clock time was to be recorded and reported for all blood draws and all subjects. A deviation greater than +/-2 minutes will be reported as a protocol deviation and its cause will be recorded.

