### 5.4. Method of Assigning Subjects to Treatments

Using SAS® 9.4, a computer-generated block-wise randomization list adequate for placebo-controlled studies was prepared by the Programming & Biostatistics Department of [REDACTED]. At each cohort, 6 subjects were randomly assigned to receive cytisine and 2 subjects randomized to receive placebo.

Upon confirmation that all eligibility criteria are met on Day 0, subjects were sequentially assigned a randomization number. The randomization number was provided to the unblinded Pharmacist on site and defined the treatment to which subjects were allocated (test or placebo) per the randomization list.

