## 8. STATISTICAL METHODS

The statistical analysis and TFLs will be done using SAS® for version 9.4.

PK parameters for cytisine ( $C_{max}$  and  $T_{max}$ ) will be estimated using non-compartmental analysis (NCA) in Phoenix® WinNonlin® version 8.1 (Pharsight Corp., Mountain View, CA).

Summaries of demographics, baseline characteristics and safety endpoints will be provided for the Safety Analysis Set, defined as all subjects who received a single dose of cytisine or placebo.

Unless otherwise indicated, numerical variables will be summarized using: number of observations (n), arithmetic mean, standard deviation, coefficient of variation (CV%), median and range (minimum and maximum). Categorical variables will be summarized with number of subjects and percentage within a treatment (dose level). Descriptive statistics will be presented with the same precision as the original data, i.e, the same number of decimals or significant digits.  $T_{max}$  is stated with the same number of significant digits as the actual sampling time. Baseline for post-dose assessments is defined as the last observation recorded before dose. Summaries will be provided for each dose level/treatment (Placebo; 6.0 mg cytisine; 9.0 mg cytisine, etc.). Unless otherwise indicated, no statistical comparisons between the cohorts are planned.

Unscheduled measurements will be listed in the individual data listings. With the

exception of baseline or unscheduled measurements performed due to an error at the scheduled measurement (e.g. equipment failure), unscheduled measurements will be excluded from the descriptive statistical analysis.

No imputation of missing data will be done, except for missing dates and/or times required for the calculation of AEs' time to onset and duration (e.g. see Section 8.7.1) and for plasma concentrations below the lower limit of quantification (LLOQ) (see Section 8.8).

Assessments for trends in dose-limiting adverse events or  $C_{max}$  levels in relationship to BMI categories/levels and baseline Nicotine Metabolite Ratio (NMR) may be explored.

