#### 8.9. Pharmacokinetic Parameters

Pharmacokinetic parameters will be estimated from the plasma concentration versus time profiles for all subjects in the pharmacokinetic analysis set.

Pharmacokinetic parameter Cmax will be calculated as the maximum observed plasma concentration (ng/mL) and Tmax will be the time to occurrence of maximum plasma concentration (h).

Individual PK parameters and descriptive statistics (number of subjects, arithmetic and geometric mean, SD, CV%, median, minimum value, and maximum value) will be presented by Cytisine Dose Level. For Cmax the 90% CI of the mean will also be

estimated. If for more than 1/3 of the subjects no reliable PK parameter could be determined, only the minimum and maximum values will be presented for that parameter and all other descriptive statistics will be omitted. Missing PK parameter data will not be imputed.

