###### **For CSR Body Text:**

The planned tables and figures for CSR body text are listed below. Other relevant tables and/or figures may be presented in the final CSR body text. Thus, the placement and numbering presented is indicative and may deviate from the placement and numbering in the final CSR body text.

[figure not shown]
In-text Tables	Title
Table A	Study Flow-Chart (to be captured from the CSP)
Table B	Identity of Investigational Products
Table C	Treatment Assignment
Table D	Subjects Disposition
Table E	Major Protocol Deviations
Table F.1	Demographic Data – Safety Analysis Set
Table F.2	Smoking History – Safety Analysis Set
Table F.3	Baseline CO – Safety Analysis Set
Table G.1	Treatment Emergent Adverse Events – All Causalities
Table G.2	Treatment Emergent Adverse Events – Related
Table H	Cytisine: $C_{max}$ and $T_{max}$ Following Administration of Cytisine (6 mg, 9 mg, 12 mg, 15 mg, 18 mg, 21 mg, 24 mg, 27 mg and 30 mg)
Table I	Cytisine: Dose Proportionality of $C_{max}$

In-text Figures	Legend
Figure A	Cytisine: Arithmetic Mean Plasma Concentration Versus Time Profile Following Administration of Cytisine (6 mg, 9 mg, 12 mg, 15 mg, 18 mg, 21 mg, 24 mg, 27 mg and 30 mg) – Linear Scale.
Figure B	Cytisine: Arithmetic Mean Plasma Concentration Versus Time Profile Following Administration of Cytisine (6 mg, 9 mg, 12 mg, 15 mg, 18 mg, 21 mg, 24 mg, 27 mg and 30 mg) – Semi-Logarithmic Scale
Figure C	Cytisine: Dose Proportionality of $C_{max}$
Figure D	Cytisine: Boxplots of $C_{max}$ as a Function of Dose

End-of-Text Tables	Title

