14.2 SAFETY DATA	
14.2.1	Treatment Emergent Adverse Events
14.2.1.1	Adverse Events Leading to Discontinuation or Withdrawal
14.2.1.2	Listings of Serious Adverse Events
14.2.1.3	Summary of Treatment Emergent Adverse Events – All Causalities
14.2.1.4	Summary of Treatment Emergent Adverse Events - Related
14.2.1.5	Summary of Treatment Emergent Adverse Events by Severity –

	All Causalities
14.2.1.6	Summary of Treatment Emergent Adverse Events by Severity – Related
14.3 PHARMACOKINETIC DATA	
14.3.1	Deviations from Blood Sampling Schedule
14.3.1.1	Deviations from Blood Sampling Schedule
14.3.1.2	Missing Blood Samples
14.3.2	Plasma Concentrations
14.3.2.1	Cytisine 6 mg: Individual Data and Descriptive Statistics of Plasma Concentrations
14.3.2.2	Cytisine 9 mg: Individual Data and Descriptive Statistics of Plasma Concentrations
14.3.2.3	Cytisine 12 mg: Individual Data and Descriptive Statistics of Plasma Concentrations
14.3.2.4	Cytisine 15 mg: Individual Data and Descriptive Statistics of Plasma Concentrations
14.3.2.5	Cytisine 18 mg: Individual Data and Descriptive Statistics of Plasma Concentrations
14.3.2.6	Cytisine 21 mg: Individual Data and Descriptive Statistics of Plasma Concentrations
14.3.2.7	Cytisine 24 mg: Individual Data and Descriptive Statistics of Plasma Concentrations
14.3.2.8	Cytisine 27 mg: Individual Data and Descriptive Statistics of Plasma Concentrations
14.3.2.9	Cytisine 30 mg: Individual Data and Descriptive Statistics of Plasma Concentrations
14.3.3	Pharmacokinetic Parameters
14.3.3.1	Cytisine 6 mg: Individual Data and Descriptive Statistics of Pharmacokinetic Parameters
14.3.3.2	Cytisine 9 mg: Individual Data and Descriptive Statistics of Pharmacokinetic Parameters
14.3.3.3	Cytisine 12 mg: Individual Data and Descriptive Statistics of Pharmacokinetic Parameters
14.3.3.4	Cytisine 15 mg: Individual Data and Descriptive Statistics of Pharmacokinetic Parameters
14.3.3.5	Cytisine 18 mg: Individual Data and Descriptive Statistics of Pharmacokinetic Parameters
14.3.3.6	Cytisine 21 mg: Individual Data and Descriptive Statistics of Pharmacokinetic Parameters
14.3.3.7	Cytisine 24 mg: Individual Data and Descriptive Statistics of Pharmacokinetic Parameters
14.3.3.8	Cytisine 27 mg: Individual Data and Descriptive Statistics of Pharmacokinetic Parameters
14.3.3.9	Cytisine 30 mg: Individual Data and Descriptive Statistics of Pharmacokinetic Parameters

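### Do different rules for BLQ concentrations in the geometric mean and in the other statistics (SAP 8.8) need changing?

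*SAP*

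**What the plan says.** Section 8.8 sets the assay limit: "The pre-planned lower limit of quantification (LLOQ) is 1 ng/mL". It then lists the summaries, one set per sampling time: "Descriptive statistics (number of subjects, geometric mean, arithmetic mean, SD, CV%, median, minimum and maximum) of the plasma concentrations will be presented for each time". BLQ values "will be taken as missing for the calculation of geometric mean and replaced by zero for calculation of the remaining summary statistics". Section 8 makes this the one stated exception to no imputation for concentrations, "for plasma concentrations below the lower limit of quantification (LLOQ) (see Section 8.8").

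The summaries go into end-of-text tables 14.3.2.1 to 14.3.2.9 (Section 9.1.1), titled for the first dose level "Cytisine 6 mg: Individual Data and Descriptive Statistics of Plasma Concentrations". The mean profiles, in-text Figures A and B and end-of-text figures 14.3.5.x, use the arithmetic mean: "Cytisine: Arithmetic Mean Plasma Concentration Versus Time Profile Following Administration of Cytisine".

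Section 8.9 limits reporting when a PK parameter cannot be determined in more than one third of subjects: "only the minimum and maximum values will be presented for that parameter and all other descriptive statistics will be omitted". That rule covers Cmax and Tmax, not concentrations. Each dose level has six subjects on active drug (Section 5.4): "At each cohort, 6 subjects were randomly assigned to receive cytisine and 2 subjects randomized to receive placebo".

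**The concern.** When all six values are quantifiable, both means describe the same six subjects. When all six are BLQ, the arithmetic mean is zero and the geometric mean is not calculable. Between these, the two means part company. The geometric mean is taken over the quantifiable subjects only, so it cannot fall below 1 ng/mL. The arithmetic mean is taken over all six, with zeros in place of values that lie between 0 and 1 ng/mL, and the zeros also inflate the CV%.

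A table could then show a geometric mean above the arithmetic mean. That is impossible on one set of positive values, and a reader might take it for a programming error. The visible text asks for one number of subjects per time point. It gives no BLQ count and no BLQ share above which the means are left out. At stake is the reading of the late, and perhaps the earliest, time points in the concentration tables, and the low ends of the mean profiles.

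**Working it through.** **Inputs from the SAP.** LLOQ 1 ng/mL (8.8); n = 6 on cytisine per dose level (5.4); the BLQ rule (8.8). The SAP gives no expected concentrations, no variability and no sampling times, so the true geometric mean and the CV are assumptions, varied below. It states no figure on this point to reproduce.

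**Direction, by algebra.** Let k of 6 values be BLQ, with 0 < k < 6.

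- Arithmetic mean under the plan = (sum of quantifiable values)/6. Each BLQ value is at least 0 and below 1, so the shortfall is less than k/6 × 1 ng/mL, at most 5/6 = 0.83 ng/mL.
- Geometric mean under the plan = exp(mean log of the 6 − k quantifiable values). Every deleted value is below every retained one, so the result is always too high.

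**When the order reverses.** If the quantifiable values were log-normal, their arithmetic mean would be √(1 + CV²) times their geometric mean. The plan multiplies that arithmetic mean by (6 − k)/6. The geometric mean is then the larger when √(1 + CV²) < 6/(6 − k), that is, CV < √((6/(6 − k))² − 1).

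- k = 1: √(1.2² − 1) = 66%
- k = 2: √(1.5² − 1) = 112%
- k = 3: √(2² − 1) = 173%

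These are approximate, because values cut off at the LLOQ are not exactly log-normal.

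**Example.** Values 1.2, 1.5, 1.8, 2.1, 2.6 and one BLQ. The five quantifiable values sum to 9.2 and multiply to 17.69. Arithmetic mean 9.2/6 = 1.53; geometric mean 17.69^(1/5) = 1.78; CV 58%. With half the LLOQ (0.5) for the sixth value: arithmetic mean 9.7/6 = 1.62, geometric mean (17.69 × 0.5)^(1/6) = 1.44, CV 45%.

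**How often, by simulation** (log-normal cohorts of six, at least 200,000 per cell). At CV 50%:

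| True geometric mean (ng/mL) | Some but not all BLQ | Geometric > arithmetic |
|---|---|---|
| 1.0 | 97% | 97% |
| 1.5 | 73% | 72% |
| 2 | 36% | 35% |
| 3 | 6% | 5% |
| 5 | 0.2% | 0.2% |
| 10 | about 0% | about 0% |

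Once some but not all values are BLQ, reversal is close to certain at CV 30% and occurs in 93% to 100% of cases at CV 50%. At CV 100% it occurs in 98%, 80%, 64% and 48% at true geometric means of 1, 2, 3 and 5. At CV 30% and a true geometric mean of 5, such cohorts hardly ever arise.

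**How large, and whether half the LLOQ is better** (cohorts with one or two BLQ values; geometric mean in ng/mL):

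| CV, true geometric mean | Uncensored | Plan | LLOQ/2 |
|---|---|---|---|
| 30%, 1.5 | 1.41 | 1.59 (+13%) | 1.26 (−10%) |
| 50%, 1.5 | 1.48 | 1.79 (+21%) | 1.34 (−9%) |
| 100%, 3 | 2.62 | 3.69 (+41%) | 2.47 (−6%) |

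Percentages are from unrounded means. In the middle row the arithmetic mean is 1.64 uncensored, 1.46 under the plan and 1.57 with half the LLOQ.

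**What uses these means.** Section 6.3 lists concentrations, Cmax and Tmax as the PK variables. Cmax and Tmax are read from each subject's own profile (8.9), and the power model is fitted to individual Cmax values (8.10). None of these passes through a per-time-point mean.

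**The case for a change.** The strongest case for a change is that the direction of both biases is certain and the remedy needs no new data. At moderate or high variability, half the LLOQ brings both means closer to the uncensored values. Leaving out means when more than a third of values are BLQ would match the share used in 8.9. A reader who meets a geometric mean above an arithmetic mean has a fair question.

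The arithmetic stands; the case for the remedy is weaker. The logarithm of zero is undefined, so any plan that sets BLQ to zero must treat the geometric mean separately, and 8.8 says openly how. Half the LLOQ is also a convention: it biases the geometric mean downward by 6% to 10% in the cases above. At CV 30% it misses by nearly as much as the plan, in the other direction, and it puts 0.5 ng/mL, a value nobody measured, into the minimum.

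A one-third omission rule would do harm. Applied to a pre-dose time point where every value is BLQ, it removes an arithmetic mean of zero and takes the starting point out of the linear mean profiles.

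What survives is the wish to see, beside each geometric mean, how many subjects it rests on. The individual values in the same tables already let a reader count them. The table shells are redacted and may show a BLQ count, so its absence cannot be asserted.

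**Conclusion.** No change to the plan is needed. At time points with some but not all values BLQ, the two means in 8.8 describe different subjects and err in opposite directions. In the cases tabulated, the geometric mean is too high by 13% to 41%; the arithmetic mean is always less than k/6 ng/mL too low. These percentages assume log-normal concentrations with true geometric means of 1.5 to 3 ng/mL, close to the limit. At CV 50% the reversal almost disappears by 5 ng/mL; at CV 100% it fades more slowly. The SAP does not show where actual concentrations lie, so the number of affected time points is unknown.

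The rule is a fair, explicit trade-off confined to descriptive output. No Cmax, Tmax, dose-proportionality or safety result changes under any alternative, and the alternative examined carries its own bias. Noting under the table how many subjects contribute to the geometric mean is a detail the programmers can settle in the shells without amending the SAP.

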#### 8.9. Pharmacokinetic Parameters

Pharmacokinetic parameters will be estimated from the plasma concentration versus time profiles for all subjects in the pharmacokinetic analysis set.

Pharmacokinetic parameter Cmax will be calculated as the maximum observed plasma concentration (ng/mL) and Tmax will be the time to occurrence of maximum plasma concentration (h).

Individual PK parameters and descriptive statistics (number of subjects, arithmetic and geometric mean, SD, CV%, median, minimum value, and maximum value) will be presented by Cytisine Dose Level. For Cmax the 90% CI of the mean will also be

estimated. If for more than 1/3 of the subjects no reliable PK parameter could be determined, only the minimum and maximum values will be presented for that parameter and all other descriptive statistics will be omitted. Missing PK parameter data will not be imputed.

#### **8.10. Dose-proportionality**

Linear-dose proportionality of  $C_{max}$  after oral administration of Cytisine 6 mg, 9 mg, 12 mg, 15 mg, 18 mg, 21 mg, 24 mg, 27 mg and 30 mg will be assessed by using an exponential regression model that measures the degree of nonlinear proportionality. The relationship is written as a power function:  $y = \alpha * \text{dose}^\beta$ , where  $y$  denotes the pharmacokinetic parameter being analyzed ( $C_{max}$ ),  $\alpha$  is a constant and  $\beta$  is the proportionality constant. Linearization of this relationship gives:

$$\log(y) = \log(\alpha) + \beta * \log(\text{dose}).$$

The relationship is dose proportional when  $\beta = 1$  (linear pharmacokinetics) or considered to be dose dependent (non-linear pharmacokinetics) when  $\beta \neq 1$ . The exponent of the power function fitted to the individual  $C_{max}$  values and 95% CI will be assessed.

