**Figure 1. Study Diagram:**

### 5.2. Number of Subjects

The study protocol defined a sample size of 8 subjects per cohort, which is consistent with standard practice in early-phase clinical trials with similar study objectives.

Considering that 9 cohorts were pre-planned, a total of 72 subjects was estimated for enrollment.

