### **8.1.3. Pharmacokinetic Analysis Set**

The Pharmacokinetic Analysis Set is defined as all subjects who received a dose of cytisine and have evaluable pharmacokinetic data.

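### Does Section 8.10 let a 95% CI for beta that contains 1 be read as proof of dose proportionality?

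*SAP*

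**What the plan says.** Section 8.10 states that proportionality of Cmax over the nine doses "will be assessed by using an exponential regression model that measures the degree of nonlinear proportionality". "The relationship is written as a power function", Cmax = alpha × dose^beta, and is made linear by taking logs. Beta equal to 1 is labelled dose proportional; the text continues "linear pharmacokinetics) or considered to be dose dependent (non-linear pharmacokinetics) when" beta is not 1. The section ends with the planned output: "The exponent of the power function fitted to the individual" Cmax values is to be assessed together with its 95% CI. It gives no reference range for beta, no hypothesis test and no rule that turns the interval into one of the two labels.

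The results go to Table I and Figure C in Section 9.1.1, both titled "Cytisine: Dose Proportionality of" Cmax. The data come from the Pharmacokinetic Analysis Set in Section 8.1.3: "all subjects who received a dose of cytisine and have evaluable pharmacokinetic data". Section 5.4 says that in each cohort "6 subjects were randomly assigned to receive cytisine and 2 subjects randomized to receive placebo". Section 5.2 supports 8 subjects per cohort as a number "which is consistent with standard practice in early-phase clinical trials with similar study objectives", with no precision target for beta.

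**The concern.** A two-way label next to a confidence interval invites a shortcut: call the drug linear if the interval contains 1 and non-linear if it does not. That shortcut treats failure to detect a departure as evidence that there is none, and it rewards imprecision, because a noisier study is more likely to be called proportional. Applied instead to the point estimate, the label would always be non-linear, since a fitted slope is never exactly 1. Neither use is sound, and the readable text excludes neither.

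At stake is one sentence in the study report. Someone has to write a conclusion beneath Table I, and a statement of linear pharmacokinetics could rest on an interval that also allows a material rise in dose-normalised Cmax across the range. Because the study was not sized for beta, the interval could be wide.

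**Working it through.** **Inputs from the SAP.** Nine doses from 6 to 30 mg in 3 mg steps (Sections 5.1 and 8.10); 8 subjects per cohort (Section 5.2), of whom 6 receive cytisine (Section 5.4); a log-log linear model with a 95% CI for beta (Section 8.10).

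**Plan's own figure.** 9 × 8 = 72, which matches the enrolment in Section 5.2. Cytisine subjects: 9 × 6 = 54, the maximum if all are evaluable.

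**Assumptions.** The SAP gives no between-subject CV for Cmax, so 20, 30 and 40% are used, with constant log-scale variance.

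**Precision of beta.**
- x = ln(dose), 6 values per dose: Sxx = 13.806, √Sxx = 3.716, df = 54 − 2 = 52, t(0.975; 52) = 2.007.
- sigma = √ln(1 + CV²); SE = sigma/√Sxx; half-width h = t × SE.
- Under proportionality, dose-normalised Cmax is the same at 30 and 6 mg. In general their ratio is 5^(beta − 1), because 30/6 = 5. The largest estimated ratio whose interval still contains 1 is therefore 5^h, and its upper limit is 5^(2h) (taking the residual SD equal to sigma).

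| CV | sigma | SE | h | 5^h | 5^(2h) |
|---|---|---|---|---|---|
| 20% | 0.198 | 0.053 | 0.107 | 1.19 | 1.41 |
| 30% | 0.294 | 0.079 | 0.159 | 1.29 | 1.67 |
| 40% | 0.385 | 0.104 | 0.208 | 1.40 | 1.95 |

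**How often the interval contains 1 when beta is not 1.** Non-central t with 52 df and non-centrality (beta − 1)/SE:

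| True beta | 30 vs 6 mg ratio | CV 20% | CV 30% | CV 40% |
|---|---|---|---|---|
| 1.10 | 5^0.10 = 1.17 | 0.547 | 0.763 | 0.843 |
| 1.15 | 5^0.15 = 1.27 | 0.211 | 0.538 | 0.705 |
| 1.20 | 5^0.20 = 1.38 | 0.043 | 0.300 | 0.527 |

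At true beta 1.15 the probability is 0.044 at CV 15%. With 5 evaluable subjects per dose (n = 45, df = 43) it is 0.291, 0.605 and 0.748 at CV 20, 30 and 40%.

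**Would a formal margin help?** Take, as an example only, a tolerated ratio of 0.80 to 1.25. This gives beta limits of 1 ± ln(1.25)/ln(5), or 0.861 to 1.139. If true beta is 1, the whole 95% CI falls inside these limits in about 45, 1 and 0% of trials at CV 20, 30 and 40%. At moderate CV or above, such a rule would almost always end as inconclusive.

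**What the wording commits to.** Set beside these figures, Section 8.10 commits to three things: a definition of what the values of beta mean, a fitted exponent, and a 95% CI. The definition is correct, and the estimate and interval are the right output for the model. The step from interval to label, which the probabilities above describe, does not appear in the text.

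**The case for a change.** The strongest case for a change is that the conclusion under Table I has to come from somewhere. The SAP supplies two labels and one interval, and the natural way to join them is the faulty one. The logical gap does not depend on the CV; only its size does. Closing it would cost one sentence, and reporting 5^(beta − 1) with its CI would show the reader how large a departure remains possible.

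Part of this stands. The text does not link the interval to the labels, and the arithmetic shows that at CV 30 to 40% an interval containing 1 is weak evidence of proportionality.

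The rest does not carry a change. Leaving a misreading unforbidden is not the same as planning it, and the sentence supports two opposite literal uses, so no rule can be attributed to it. Section 8.10 describes the model as measuring a degree of departure, which points to estimation. The ratio 5^(beta − 1) re-expresses the same estimate and can be worked out from Table I. The missing precision basis is not a fault in a Phase 1 escalation study in which beta is supportive. The table shells are redacted and the protocol is not at hand, so an interpretive note may already exist in either.

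**Conclusion.** No change to the plan is needed. Followed as written, Section 8.10 yields a valid estimate of beta and a valid 95% CI, and the suggested caveat would alter no number in the report. The analysis is supportive: the primary objective is tolerability and safety (Section 4.1), the secondary concerns Cmax levels linked to dose-limiting adverse events (Section 4.2), and escalation was decided by safety review (Section 5.1). The interval itself, the individual values and per-dose summaries of Cmax (Section 8.9) and the boxplots (Figure D) show any imprecision to the reader.

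The figures of 21, 54 and 70% show how little an interval containing 1 would establish at CV 20, 30 and 40% if true beta were 1.15. They rest on an assumed CV, a chosen beta and full evaluability, and they are not error rates of a rule in this SAP. What remains is a gap that a competent analyst fills when writing the report: beta and its CI are described as estimates, and an interval containing 1 is reported as no departure detected. Saying so in the SAP would be harmless and is optional.
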